### **6.11.2. Prohibited Medications and Non-Drug Therapies**

Subjects may not receive the following treatments from 4 weeks prior to screening until the final follow-up visit:

- Intranasal steroids

- Inhaled corticosteroid (ICS) with or without a long acting beta-2-agonist (LABA)
- Non-ICS controller asthma medications (i.e. leukotriene modifier, methylxanthines).

Use of long-acting antihistamines within 7 days' or short-acting antihistamines within 72 hours prior to BAC, NAC or ID challenge is prohibited.

Subjects are prohibited from taking systemic corticosteroids within 6 weeks prior to screening.

Subjects must abstain from taking prescription or non-prescription drugs (including vitamins and dietary or herbal supplements) except as described in Section [6.11.1](#) within 7 days prior to the first dose of study medication until completion of the follow-up visits, unless in the opinion of the investigator and sponsor the medication will not interfere with the study.

## 7. STUDY ASSESSMENTS AND PROCEDURES

Protocol waivers or exemptions are not allowed with the exception of immediate safety concerns. Therefore, adherence to the study design requirements, including those specified in the Time and Events Table, are essential and required for study conduct.

This section lists the procedures and parameters of each planned study assessment. The exact timing of each assessment is listed in the Time and Events Table Section [7.1](#)

The following points must be noted:

- If assessments are scheduled for the same nominal time, THEN the assessments should occur in the following order:

1. 12-lead ECG
2. vital signs
3. blood draws.

Note: The timing of the assessments should allow the blood draw to occur at the exact nominal time.

- The timing and number of planned study assessments, including safety, pharmacokinetic, pharmacodynamic/biomarker assessments may be altered during the course of the study based on newly available data to ensure appropriate monitoring. Similarly the timing of the post-treatment allergen challenges may change based on new information acquired during the course of the study.
- Details of the order of planned assessments for each visit and the time windows around these visits and assessments will be given in the SRM.
- The change in timing or addition of time points for any planned study assessments must be documented in a Note to File which is approved by the relevant GSK study team member and then archived in the study sponsor and site study files, but this will not constitute a protocol amendment.

- The Institutional Review Board (IRB)/Independent Ethics Committee (IEC) will be informed of any safety issues that require alteration of the safety monitoring scheme or amendment of the Informed Consent Form.
- No more than 500 mL of blood will be collected over the duration of the study, including any extra assessments that may be required.

## 7.1. Time and Events Tables

### 7.1.1. Time and Events Table – Screening Visit(s)

Procedure	Screening Visit 1 (up to Day -28)	Screening Visit 2 (up to Day -3))	24 hours after Screening Visit 2 (Day -20 to Day -2)	Notes
Informed consent signing	X			Includes genetics consent
Inclusion and exclusion criteria/eligibility review	X	X		
Demographics	X			
Medical history (including substance usage and family history of premature CV disease)	X			
Past and current medical conditions including cardiovascular medical history	X			
Concomitant medication review	X			
Full physical exam including height and weight	X			
Urine drug/alcohol screen	X			
Urine or serum pregnancy test (all females)	X			No women of childbearing potential are being enrolled. However this test is needed to confirm pregnancy status at screening.
Serum FSH and estradiol for post-menopausal females	X			
HIV, Hep B and Hep C screen	X			
Laboratory assessments (including liver chemistries, haematology, clinical chemistry and urinalysis)	X			
Screening Spirometry assessment	X			To confirm $FEV_1 > 70\% \text{ predicted}$
SAE Collection	X	X	X	
12-lead ECG	X			
Vital signs	X			
Skin prick test	X			To confirm eligibility
FeNO measurement	X		X	Collected prior to sputum induction
Saline and incremental BAC challenge plus associated spirometry measurements		X		Including pre-procedure $FEV_1$ assessment and repeat $FEV_1$ measurements up to 10 hours post BAC

Procedure	Screening Visit 1 (up to Day -28)	Screening Visit 2 (up to Day -3))	24 hours after Screening Visit 2 (Day -20 to Day -2)	Notes
Sputum induction and processing for BAC associated sample collection	X		X	There must be a minimum of 48 hours between 'Screening Visit 1' and 'Screening Visit 2'. This ensures adherence to a minimum 3-day window between sputum inductions. There must be a minimum of 48 hours between '24 hours after Screening Visit 2' and 'Dosing Visit 1'
Laboratory assessments (haematology only)		X	X	Blood samples should be taken pre-BAC on SV2 and on the following day at 24 hrs post BAC
Blood samples for PBMC preparations		X		Blood samples for PBMC preparations (pre-BAC and 6 hours after BAC at screening visit 2)
Provide diary card, PEF meters, rescue medication and thermometers to subjects		X		Only given out to subjects who are eligible following the BAC. Thermometers are to be given to record temperature as part of capturing AE information.
Nasal lavage			X	Collect nasal lavage to provide a background sample. Repeat nasal lavage pre-NAC, then again 5 minutes and at least 6 hours post-NAC.
Nasal filter collection			X	Collect nasal filter sample to provide a background pre-wash sample, after nasal wash repeat nasal filter sampling pre-NAC, then again 5 minutes and at least 6 hours post-NAC.
NAC			X	Commence after the 24-hour BAC sputum and blood biomarker samples have been taken. Only to be done once subjects have completed a successful BAC.
ID challenge			X	ID challenge to be administered after NAC. Measurements to be made 15 minutes and 6 hours post ID challenge.
Nasal scrape			X	Nasal mucosa sample to be collected at least 6 hours post-NAC.

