### 4.2. Treatment Arms and Duration

- The study will consist of a screening period of up to approximately 4 weeks (involving two screening visits), a blinded treatment period of 8 weeks, followed by a follow-up period of up to 3 months. The total duration of the study for each subject will therefore be a maximum of approximately 6 months. All doses will be administered in the clinic.
- Approximately 24 subjects per treatment arm will be randomised in a 1:1 ratio to receive either i.n. 20ng GSK2245035 or placebo every week for the duration of 8 weeks.

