#### 7.1.1 Time and Events Table – Screening Visit(s)

Procedure	Screening Visit 1 (Day -28 to Day -22)	Screening Visit 2 (Day -21 to Day -3)	24 hours after Screening Visit 2 (Day -20 to Day -2)	Notes
Informed consent signing	X			Includes genetics consent
Inclusion and exclusion criteria/eligibility review	X	X		
Demographics	X			
Medical history (including substance usage and family history of premature CV disease)	X			
Past and current medical conditions including cardiovascular medical history	X			
Concomitant medication review	X			
Full physical exam including height and weight	X			
Urine drug/alcohol screen	X			
Urine or serum pregnancy test (all females)	X			No women of childbearing potential are being enrolled. However this test is needed to confirm pregnancy status at screening.
Serum FSH and estradiol for post-menopausal females	X			
HIV, Hep B and Hep C screen	X			

Procedure	Screening Visit 1 (Day -28 to Day -22)	Screening Visit 2 (Day -21 to Day -3)	24 hours after Screening Visit 2 (Day -20 to Day -2)	Notes
Laboratory assessments (including liver chemistries, haematology, clinical chemistry and urinalysis)	X			
Screening Spirometry assessment	X			To confirm FEV 1 >70% predicted
SAE Collection	X	X	X	
12-lead ECG	X			
Vital signs	X			
Skin prick test	X			To confirm eligibility
FeNO measurement	X		X	Collected prior to sputum induction
Saline and incremental BAC challenge plus associated spirometry measurements		X		Including pre-procedure FEV 1 assessment and repeat FEV 1 measurements up to 10 hours post BAC
Sputum induction and processing for BAC associated sample collection	X		X	Sputum inductions must be separated by at least 3 days
Laboratory assessments (haematology only)		X	X	Blood samples should be taken pre-BAC on SV2 and on the following day at 24 hrs post BAC
Blood samples for PBMC preparations		X		Blood samples for PBMC preparations (pre-BAC and 6 hours after BAC at screening visit 2)
Provide diary card, PEF meters, rescue medication and thermometers to subjects		X		Only given out to subjects who are eligible following the BAC. Thermometers are to be given to record temperature as part of capturing AE information.
Nasal lavage			X	Collect nasal lavage to provide a background sample. Repeat nasal lavage pre-NAC, then again 5 minutes and at least 6 hours post-NAC.

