8.4.2.2.1 Nasal Lavage Fluid & Nasal Lavage Filters

Nasal Lavage Fluid samples are expected to provide the Mast Cell Mediator results (plus ECP and allergen specific IgA). Nasal Filters are expected to provide the Inflammatory mediators (chemokines and cytokines).

Statistical Analysis of “Background” Samples

- Additional Figures of type PD_F3
- Separate Bayesian repeated measures mixed effect models (per analyte), with non-informative priors for all model parameters, will be fitted to each transformed response over the planned post Screening time points (FUV1 and FUV2).
- Baseline: (Transformed) SV Background
- The additional terms to include in the chosen “R” model (see Section 11.9.1) are:

Fixed Categorical: Intercept

Fixed Continuous Covariates: Baseline*Visit

The repeated measures term is Visit (Subject = Subject), with an Unstructured variance covariance matrix common to each treatment arm (2x2).

Statistical Analysis of “Direct NAC effect” Samples

- Additional Figures of type PD_F2 and PD_F4
- Separate Bayesian repeated measures mixed effect models (per analyte), with non-informative priors for all model parameters, will be fitted to each of the transformed responses collected from an individual subject (i.e. 6 data points per subject; the combinations of Visit and Sample times SV Pre-NAC, SV Post NAC, FUV1 Pre-NAC, FUV1 Post NAC, FUV2 Pre-NAC and FUV2 Post NAC; where Post-NAC is either 5m or 6h depending whether the biomarker is a mast cell mediator (5m) or inflammatory (6h)).
- For the purposes of assessing models R1 to R3 (see Section 11.9.1) consider “Visit” in those models to be a six level term covering the data recorded per subject with these additional terms:

Fixed Categorical: Intercept

The repeated measures term is Visit (Subject = Subject), with an Unstructured variance covariance matrix common to each treatment arm (6x6).

- In this model parameterization the usual “Baseline” timepoints (Pre-NACs) are modeled as response variables and not covariates. Therefore posterior distributions for the quantities of interest; namely treatment effect on “within visit fold changes (Post/Pre) adjusted for the screening visit and placebo fold changes”; use fold changes representing the mean predicted response at the timepoint (and not the average of the individual subjects fold changes).

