
 Reporting for tables, figures and formal statistical analyses : 
 Planned time relative to dosing will be used in figures, summaries, statistical analyses and calculation of any derived parameters, unless otherwise stated. The impact of any major deviation from the planned assessment times and/or scheduled visit days on the analyses and interpretation of the results will be assessed as appropriate. Reporting for Data Listings: 
 Planned and actual time relative to study drug dosing will be shown in listings (Refer to IDSL Statistical Principle 5.05.1). Unscheduled or unplanned readings will be presented within the subject's listings. Visits outside the protocol defined time-windows (i.e. recorded as protocol deviations) will be included in listings but omitted from figures, summaries and statistical analyses.

Reporting Standards								
Unscheduled Visits								

 • Unscheduled visits will not be included in summary tables. • Unscheduled visits will not be included in figures. • All unscheduled visits will be included in listings. 								
Descriptive Summary Statistics								
Continuous Data	Refer to IDSL Statistical Principle 6.06.1							
Categorical Data	N, n, frequency, %							
Reporting of Pharmacokinetic Concentration Data								
Descriptive Summary Statistics	Refer to IDSL Statistical Principle 6.06.1 Assign zero to NQ values (Refer to GUI_51487 for further details)							
Graphical Displays								

 • Refer to IDSL Statistical Principles 7.01 to 7.13. • Where possible the following colour scheme will be adopted noting that treatment comparisons against Placebo will utilise the style of GSK2245035 treatment: 								
Treatment Colour Plotting Symbol Line Style								
Placebo once weekly	Blue	Circle, Solid	Solid					
20 ng GSK2245035 i.n. once weekly	Orange	Triangle (up), Solid	Solid					
If applicable, eg individual subject profile plots, a different line style can be applied to distinguish Allergen Exposure in the Efficacy Figures.								
Treatment Allergen Exposure Strata Colour Plotting Symbol Line Style								
Placebo once weekly	Presumed	Blue	Circle, Solid	Solid				
	Unknown	Blue	Circle, Hollow	ShortDash				
20 ng GSK2245035 i.n. once weekly	Presumed	Orange	Triangle (up), Solid	Solid				
	Unknown	Orange	Triangle (up), Hollow	ShortDash				

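### The screening table lets Screening Visit 2 fall on Day -26 to Day -22, but the visit 24 hours later is still confined to Day -20 to Day -2, and the SAP omits out-of-window visits from analysis

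*Protocol*

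**What the plan says.** Protocol 7.1.1 sets out screening in three columns:

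- "Screening Visit 1 (up to Day -28")
- "Screening Visit 2 (up to Day -3")
- "24 hours after Screening Visit 2 (Day -20 to Day -2")

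The notes add a spacing rule: "There must be a minimum of 48 hours between 'Screening Visit 1' and 'Screening Visit 2". Protocol 4.2 describes "a screening period of up to approximately 4 weeks (involving two screening visits"). Section 7 allows no waivers except for immediate safety concerns and treats adherence to the Time and Events Table as required. It also says that time windows around visits will be given in the Study Reference Manual (SRM).

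The third column holds the 24-hour post-challenge exhaled nitric oxide, sputum and haematology. It also holds the screening nasal lavage and nasal filter samples, the nasal allergen challenge (NAC), the intradermal challenge and the nasal scrape.

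SAP 11.4.3 states: "Visits outside the protocol defined time-windows (i.e. recorded as protocol deviations) will be included in listings but omitted from figures, summaries and statistical analyses". SAP 11.2.1 makes Data Management responsible for the windows. It says that items outside them may be transferred as unscheduled, with the planned item left empty, and are to be captured as deviations. SAP 8.4.2.2.1 uses a sample from the third-column visit as the model covariate: "Baseline: (Transformed) SV Background".

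**The concern.** The third column is not a free-standing visit. It is tied to 24 hours after Screening Visit 2 (SV2), so its range should be the SV2 range moved by one day. The SV2 heading now has no earliest day of its own, while the next-day heading still opens at Day -20. A site that places SV2 early in the permitted period meets the SV2 heading and then cannot meet the next one.

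If the printed window is applied literally, the next-day visit is a deviation and its data leave the analyses. These are pre-treatment samples that cannot be collected again. Four uses are exposed:

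- the covariate in the nasal background models (SAP 8.4.2.2.1);
- the screening fold change that is subtracted in the direct bronchial and nasal challenge analyses (SAP 8.4.2.1 and 8.4.2.2.1);
- intradermal change from baseline, which SAP 11.4.2.2 leaves underived when baseline is missing;
- eight of the thirteen lettered responder questions in SAP Table 15 (E and G to M), where a missing endpoint takes the subject out of the denominator.

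**Working it through.** **Inputs.** All are from Protocol 7.1.1 unless noted.

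- Screening Visit 1 (SV1): up to Day -28, read as no earlier than Day -28. The screening period of about 4 weeks in Protocol 4.2 supports this reading.
- SV1 to SV2: at least 48 hours, i.e. 2 days.
- SV2: Day -3 at the latest.
- Next-day visit: SV2 + 1 day, with stated window Day -20 to Day -2.
- Planned randomisation: about 24 per arm, 48 in all (Protocol 4.2).

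**Origin of the stated window.** Before Amendment 4 the column read "Screening Visit 2 (Day -21 to Day -3"). Adding one day gives Day -20 to Day -2, exactly the range still printed. The amendment log in Protocol Appendix 7 shows that Amendment 4 changed the SV1 and SV2 headings and left the next-day range as it was. The log is used here only to trace the source; the conflict itself lies in the current table.

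**Current text.** Earliest SV2 = Day -28 + 2 = Day -26. Permitted SV2 days run from Day -26 to Day -3, which is 24 days. The next-day visit then runs from Day -25 to Day -2, against a window of Day -20 to Day -2 (19 days).

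| SV2 | Next-day visit | Days before window opens |
|---|---|---|
| Day -26 | Day -25 | 5 |
| Day -25 | Day -24 | 4 |
| Day -24 | Day -23 | 3 |
| Day -23 | Day -22 | 2 |
| Day -22 | Day -21 | 1 |
| Day -21 to -3 | Day -20 to -2 | within window |

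**Dependence on SV1.** SV1 on Day -28 leaves 5 conflicting SV2 days, Day -27 leaves 4, Day -26 leaves 3, Day -25 leaves 2 and Day -24 leaves 1. From Day -23 onward there are none. Because the screening period is only approximately 4 weeks, SV1 on Day -30 would leave 7.

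**Share of subjects.** The documents give no distribution of visit days, so each line below is an assumption.

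1. SV2 spread evenly over its 24 days: 5/24 = 20.8%; 0.208 × 48 = 10.
2. All permitted SV1 and SV2 day pairs equally likely. SV1 can run from Day -28 to Day -5, giving 24 + 23 + … + 1 = 300 pairs, of which 5 + 4 + 3 + 2 + 1 = 15 conflict: 15/300 = 5%; 0.05 × 48 = 2.4.
3. SV1 uniform over its 24 days, then SV2 uniform over the days that remain: (5/24 + 4/23 + 3/22 + 2/21 + 1/20)/24 = 0.664/24 = 2.8%; 0.028 × 48 = 1.3.

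These are illustrations, not bounds. If no SV2 fell before Day -21, nobody would be affected.

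**The case against.** The headings can all be met together: an SV2 on Day -21 to Day -3 satisfies every column and both 48-hour rules. That is true, and it confines the conflict to SV1 on Day -24 or earlier with SV2 on Day -26 to Day -22. But nothing in the SV2 heading tells a site to avoid those days.

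The loss of data also depends on documents not available here. The SRM may hold further windows, Section 7 lets timing changes be made by Note to File, and Data Management implements the windows. SAP Table 11 labels these samples by time since challenge, not by study day. A tolerance of five days or more would prevent the omission when SV1 is on Day -28 or later. This stands as a condition on the consequence. No such tolerance appears in the protocol or SAP, and one would not remove the printed mismatch.

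The SAP rests on Amendment 2, when the SV2 and next-day ranges agreed. That is correct, but the next-day range was the same then, so a visit on Day -25 to Day -21 is out of window on either version.

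A reader might infer that about a fifth of the trial would lose all its screening data from this visit. The documents do not support that. The fifth comes from one assumed spread, and other reasonable spreads give 3% or 5%. Subjects screened before Amendment 4 had consistent windows. The data also stay in listings. SAP 11.6.2.3 treats missing responses as missing at random, which covers the direct challenge models, and handles missing covariates case by case, by omission or imputation. SAP 11.4.2.1 labels the intradermal baseline Screening Visit 2 although the protocol places it the next day, and modelling of that endpoint is conditional in any case.

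**Conclusion.** The current table contradicts itself for SV2 on Day -26 to Day -22. The next-day visit then falls 1 to 5 days before its window opens. Applied literally, the SAP leaves those screening samples out of the exploratory analyses.

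The expected effect is loss of precision, not bias between arms. The screening days are fixed before randomisation at Dosing Visit 1, so the omission cannot depend on assigned treatment.

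A reader might also infer that the primary analysis is at risk. It is not under the windows now in force: the baseline for both the late and early asthmatic responses is the SV2 challenge itself (SAP 11.4.2.1), and SV2 on these days meets its current heading.

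The size is unknown: about 3% to 21%, or 1 to 10 of 48, under the spreads shown, and only for subjects screened under Amendment 4. The conclusion rests on reading Day -28 as the earliest day for SV1 and on there being no sufficient tolerance in the SRM or data-management windows. The point is minor, but the inconsistency is definite.

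**What to change.** Reconcile the SV2 and next-day headings in Protocol 7.1.1 so that every permitted SV2 day has a permitted visit 24 hours later. Which of the two ranges should change is for the sponsor to decide.

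Align the SRM and the data-management windows used under SAP 11.2.1 with the result, so that samples taken 24 hours after a compliant SV2 are not treated as out of window. For subjects already screened under Amendment 4, check whether any next-day visit fell before Day -20 and how it was classified.

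The cost is a heading edit at the next amendment and a matching window setting. No visit or procedure needs to be added.

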		Visit	"T&E" descriptions of within Visit Sampling Times	Visit	Planned Time
Nasal lavage	Changes over time (Background timepoint)	SV2 (24h)	Background	SV	Background
			Pre-NAC		Pre-NAC
			NAC+5m		5m Post NAC
			NAC+6h		6h Post NAC
	Direct NAC effects	FUV1 (24h)	Background	FUV1	Background
			Pre-NAC		Pre-NAC
			NAC+5m		5m Post NAC
			NAC+6h		6h Post NAC
	TLR7 Induced changes (confirm target engagement)	FUV2 (24h)	Background	FUV2	Background
			Pre-NAC		Pre-NAC
			NAC+5m		5m Post NAC
			NAC+6h		6h Post NAC
Nasal filter collection	Changes over time (Background timepoint)	DV1	Pre-Dose	DV1	Pre-Dose
			Dose+24h		24h Post Dose
		DV4	Pre-Dose	DV4	Pre-Dose
			Dose+24h		24h Post Dose
	Direct NAC effects	DV8	Pre-Dose	DV8	Pre-Dose
			Dose+24h		24h Post Dose
		SV2 (24h)	Background	SV	Background
			Pre-NAC		Pre-NAC
			NAC+5m		5m Post NAC
			NAC+6h		6h Post NAC
	FUV1 (24h)	Background	FUV1	Background	Background
		Pre-NAC		Pre-NAC	Pre-NAC
		NAC+5m		5m Post NAC	5m Post NAC
		NAC+6h		6h Post NAC	6h Post NAC

T&E procedure	"Informal" description / rationale for samples	T&E Timepoints		Data Display Labelling for Statistical Modelling activities/outputs		
		Visit	"T&E" descriptions of within Visit Sampling Times	Visit	Planned Time	
		FUV2 (24h)	Background	FUV2	Background	
Nasal scrape	Changes over time		Pre-NAC		Pre-NAC	
			NAC+5m		5m Post NAC	
			NAC+6h		6h Post NAC	
Genetic sample	PGx	SV2 (24h)	NAC+6h	SV	6h Post NAC	
		FUV1 (24h)	NAC+6h	FUV1	6h Post NAC	
		FUV2 (24h)	NAC+6h	FUV2	6h Post NAC	
Genetic sample	PGx	1x at any of DV1-DV8	n/a	n/a	n/a	
Blood sample for biomarker analysis	TLR7 Induced changes (confirm target engagement)	DV1	Pre-Dose	DV1	Pre-Dose	
			Dose+24h		24h Post Dose	
		DV8	Pre-Dose	DV8	Pre-Dose	
			Dose+24h		24h Post Dose	
Blood sample for RNA analysis	TLR7 induced gene changes in the periphery	DV1	Pre-Dose	DV1	Pre-Dose	
		DV8	Dose+24h	DV8	24h Post Dose	
		FUV2 (Wk 12)	Pre-BAC	FUV2	Pre-BAC	
FeNO measurement	Treatment induced FeNO changes	All Dosing Visits (DV1 to DV8 inclusive)	Pre-Dose	DV1, DV2, DV3, etc..., DV8	Pre-Dose	
		SV1	Prior to Sputum	SV	Pre-BAC	
	BAC induced FeNO changes	SV2 (24h)	BAC+24h		24h Post BAC	
		FUV1 (Wk 9)	Pre-BAC	FUV1	Pre-BAC	
		FUV1 (24h)	BAC+24h		24h Post BAC	
		FUV2 (Wk 12)	Pre-BAC	FUV2	Pre-BAC	
		FUV2 (24h)	BAC+24h		24h Post BAC	
		FUV3 (Wk 20)	Pre-BAC	FUV3	Pre-BAC	
		FUV3 (24h)	BAC+24h		24h Post BAC	

Table 12 Overview of Biomarkers: Types of samples, data vendors and expected analytes

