8.4.2.1.4 FeNO (Exhaled Nitric Oxide)

This section has been written assuming that FeNO response will require a log transformation. If it is not the case then appropriate modification should be made (e.g. comparisons expressed as differences rather than ratios (fold changes)).

Statistical Analysis of “Direct BAC effect” FeNO Samples

- Tables of descriptive summary statistics and Figures of type PD_F1, PD_F2 and PD_F4
- A Bayesian repeated measures mixed effect model, with non-informative priors for all model parameters, will be fitted to each of the transformed responses collected from an individual subject (i.e. 8 data points per subject; the combinations of Visit and Sample times SV Pre-BAC, SV 24 Post BAC, FUV1 Pre-BAC, FUV1 24h Post BAC, FUV2 Pre-BAC, FUV2 24h Post BAC, FUV3 Pre-BAC and FUV3 24h Post BAC).
- For the purposes of assessing models R1 to R3 (see Section 11.9.1) consider “Visit” in those models to be a eight level term covering the data recorded per subject with these additional terms:

Fixed Categorical: Intercept

The repeated measures term is Visit (Subject = Subject), with an Unstructured variance covariance matrix common to each treatment arm (8x8).

- In this model parameterization the usual “Baseline” timepoints (Pre-BACs) are modeled as response variables and not covariates. Therefore posterior distributions for the quantities of interest; namely treatment effect on “within visit fold changes (Post/Pre) adjusted for the screening visit and placebo fold changes”; use fold changes representing the mean predicted response at the timepoint (and not the average of the individual subjects fold changes).
- The model can provide several layers of useful information that should be presented instead of the default set of comparisons. The following should be modified if the model form is “R1”. The Back transformed predicted response for each treatment arm (x2) and visit (x8) combination should be produced. The next stage is to determine the fold change of the predicted response (Predicted Post BAC / Predicted Pre-BAC) within each of the four visits (SV, FUV1, FUV2 and FUV3) for each treatment. For each treatment arm its respective SV fold change can be subtracted from the FUV1, FUV2 and FUV3 visits. This quantity can then be compared across the treatment arms (within each of FUV1, FUV2 and FUV3); to provide an estimate of the screening visit and placebo adjusted change in BAC induced response.

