8.4.2.3.5 FeNO (Exhaled Nitric Oxide)

This section has been written assuming that FeNO response will require a log transformation. If it is not the case then appropriate modification should be made (e.g. comparisons expressed as differences rather than ratios (fold changes)).

Statistical Analysis of “Treatment induced changes” FeNO Samples

- Tables of descriptive summary statistics and Figures of type PD_F1 (but modified to use the PD_F3 axis layouts; i.e. one panel per subject with visit as the x-axis category and join the pre-dose values together for each subject across visits) and PD_F3.
- A Bayesian repeated measures mixed effect model, with non-informative priors for all model parameters, will be fitted to each of the post DV1 transformed responses collected from an individual subject (i.e. 7 data points per subject; the Pre-Dose values for DV2 to DV8 inclusive).
- Baseline: (Transformed) DV1 Pre-Dose
- The additional terms to include in the chosen “R” model (see Section 11.9.1) are:

Fixed Categorical: Intercept

Fixed Continuous Covariates: Baseline*Visit

The repeated measures term is Visit (Subject = Subject), with an Unstructured variance covariance matrix common to each treatment arm (7x7).

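### The screening pre-challenge FeNO is taken 2 to 25 days before the bronchial challenge, so the screening change that the SAP subtracts from follow-up is not a 24-hour challenge effect

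*Protocol*

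**What the plan says.** Protocol 7.1.1 schedules screening FeNO at SV1 and at the session 24 hours after SV2, with the note "Collected prior to sputum induction". No FeNO is scheduled at SV2, the day of the screening BAC. The visit columns read "Screening Visit 1 (up to Day -28", "Screening Visit 2 (up to Day -3" and "24 hours after Screening Visit 2 (Day -20 to Day -2" (each quote stops before the closing bracket). The notes column adds "There must be a minimum of 48 hours between 'Screening Visit 1' and 'Screening Visit 2".

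Protocol 7.1.3 schedules follow-up FeNO on the challenge day itself (Weeks 9, 12 and 20) and again 24 hours later.

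SAP Table 11 (Section 8.4.1) gives the source of the screening value as SV1, "Prior to Sputum", but displays it as visit SV, planned time Pre-BAC. The follow-up Pre-BAC values in the same table come from the challenge visits.

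SAP 8.4.2.1.4 forms a post/pre fold change within each of SV, FUV1, FUV2 and FUV3, and then states: "For each treatment arm its respective SV fold change can be subtracted from the FUV1, FUV2 and FUV3 visits". The result is compared between arms. The section names the within-visit fold change, adjusted for screening and placebo, as the quantity of interest, and presents it in place of the SAP's default comparisons.

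**The concern.** The subtraction has its intended meaning only if the screening and follow-up fold changes measure the same thing: FeNO 24 hours after a challenge relative to FeNO just before it. At follow-up they do. At screening, the change also contains whatever FeNO did between SV1 and the challenge. Protocol 4.4 itself says that natural aeroallergen exposure may fluctuate with the allergen and the time of year.

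Two things are at stake for this endpoint. The first is precision, because extra screening variation enters every adjusted comparison. The second is meaning, because a change over several days or weeks is reported as challenge-induced.

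The schedule treats other markers consistently. Haematology and PBMC samples are drawn before the challenge at SV2 and on the challenge day at follow-up. Pre-challenge sputum is taken on an earlier day at screening and at follow-up alike. Only FeNO pairs an earlier-day value at screening with same-day values at follow-up.

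**Working it through.** **Interval between the paired FeNO values**

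Inputs from Protocol 7.1.1: earliest SV1 Day -28; latest SV2 Day -3; latest post-challenge session Day -2; minimum SV1-to-SV2 gap 48 hours.

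- Minimum, SV1 to post-challenge session: 48 h + 24 h = 72 h = 3 days. This reproduces the 3-day minimum that the protocol states for the two sputum inductions held at the same sessions.
- Minimum, SV1 to challenge: 48 h = 2 days.
- Maximum, SV1 to challenge: -3 - (-28) = 25 days.
- Maximum, SV1 to post-challenge session: -2 - (-28) = 26 days.
- Follow-up pair (7.1.3): about 1 day at each of FUV1, FUV2 and FUV3.

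The SAP was written against Protocol Amendment 2. Its windows (SV1 Day -28 to -22, SV2 Day -21 to -3, inductions at least 3 days apart) give the same 2 to 25 days from SV1 to challenge.

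**Effect on precision**

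The documents give no FeNO variance or correlation, so this step rests on assumptions. Work on the log scale with a common SD s and n per arm. Let r be the correlation over 24 hours and q the correlation over the SV1-to-post-challenge gap. Treat the screening and follow-up changes as independent. This approximates the SAP's calculation, which subtracts back-transformed fold changes.

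- As scheduled: Var = (2/n) × [2s²(1 - r) + 2s²(1 - q)]
- With a same-day SV2 value: Var = (2/n) × 4s²(1 - r)
- SE ratio (same-day / scheduled) = √{2(1 - r) / [(1 - r) + (1 - q)]}

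Both s and n cancel. Take r from 0.5 to 0.8 and q from 0 to 0.5:

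| r (24 h) | q (screening gap) | SE ratio | SE reduction |
|---|---|---|---|
| 0.5 | 0.5 | √(1.0/1.0) = 1.000 | 0% |
| 0.5 | 0 | √(1.0/1.5) = 0.816 | 18% |
| 0.8 | 0.5 | √(0.4/0.7) = 0.756 | 24% |
| 0.8 | 0 | √(0.4/1.2) = 0.577 | 42% |

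The ratio falls as r rises and as q falls, so the corners bound the range at 0 to 42%. For a subject whose SV1 is only days before SV2, q would be close to r. With r = 0.7 and q = 0.65 the ratio is √(0.6/0.65) = 0.961, a reduction of 3.9%.

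**Bias**

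The screening measurements precede randomisation and follow one schedule in both arms. Expected drift between SV1 and the post-challenge value is therefore the same in each arm and cancels in the between-arm difference.

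**The case against.** The case for leaving the plan alone has several parts.

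- **The endpoint is exploratory.** No hypotheses are tested, and the LAR and EAR endpoints are untouched. This stands and limits the weight of the point.
- **The SAP is open about the source and permissive about the subtraction.** Table 11 shows SV1 as the origin, the SAP says the screening change can be subtracted, and the unadjusted within-visit fold changes are produced first for each arm. This stands in part. However, the between-arm comparison is described only for the adjusted quantity, and showing the source does not make the pair a 24-hour one.
- **The longest gaps are worst cases.** The maxima read the visit windows at their limits, and Protocol Section 7 leaves detailed windows to the Study Reference Manual, which is not among the documents. This stands for the upper ends of the ranges. The minimum of 3 days against about 1 day remains.
- **The gain may be nil.** If FeNO correlates as well over the screening gap as over 24 hours, a same-day value gains no precision. This stands, and is why the range starts at zero.
- **Section 7 already allows timing changes by Note to File.** That makes the change easy but does not make it.

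A reader might also infer a second problem in the treatment-phase FeNO model (SAP 8.4.2.3.5), which specifies "Baseline: (Transformed) DV1 Pre-Dose". Under the minimum gaps, that value can fall 72 hours after the bronchial challenge and 48 hours after the nasal one. It is tempting to call it a disturbed baseline and to add SV1 FeNO as a second covariate. The documents do not support this. Nothing in them shows that FeNO is still altered at those times, and DV1 pre-dose follows the SAP's general rule of using the latest pre-dose assessment. A worthwhile gain from the extra covariate would need SV1 to predict on-treatment values nearly as well as DV1 does, which conflicts with the loss of correlation over time that makes the SV1 timing costly here.

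**Conclusion.** The point holds for the exploratory endpoint of FeNO change after BAC. The screening pair spans 3 to 26 days and each follow-up pair about 1 day, yet the SAP labels and uses them as like quantities. The day ranges follow from the protocol's own windows, reading Day -28 as the earliest SV1 and Day -3 as the latest SV2.

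The consequence is possible loss of precision in the screening-adjusted comparison and a screening change that cannot be read as challenge-induced. It is not bias in the treatment contrast, which a reader might infer from the mismatch; the common pre-randomisation schedule rules that out in expectation. The 0 to 42% range for the standard error is conditional on the assumed correlations and on independence of the screening and follow-up changes. It applies only where the subtraction is made.

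**What to change.** 1. In Protocol 7.1.1, move the SV1 FeNO measurement to SV2 before the challenge, or take it there as well. Section 7 allows a change of timing or an added time point by Note to File without an amendment.
2. In SAP Table 11, make the SV2 pre-challenge reading the screening Pre-BAC FeNO value. Section 8.4.2.1.4 then compares 24-hour pairs at all four visits.
3. For subjects already screened without that reading, present the between-arm comparison of follow-up fold changes without the screening subtraction alongside the adjusted one.

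The cost is one breath test moved or repeated on a device already in use, one changed row in Table 11 and one further comparison from a model already planned. The treatment-phase FeNO model does not use the SV1 value, so moving the test would not affect it.
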